## **11.2 Retention of Study Documents at the Site**

### **11.2.1 eCRF Data**

If a site closes before the study has been completed, the investigator will continue to have read-only access to the eCRF. If a site closes after the study has been completed, the investigator will no longer have read access to the eCRF. Instead, each site will be provided with a CD-ROM containing the data related to the site (including eCRF data, queries, and the audit trail). As a CD-ROM is not considered a durable medium and may therefore not be

readable for the full retention period (for example, 15 years [if required by the applicable regulatory requirements]), it is possible for the investigator to request a new CD-ROM with the data related to the site.

### **11.2.2 Other Study Documents**

The investigator must keep the investigator's set of documents in the investigator TMF for at least 15 years after the *Clinical Study Report* has been approved or in accordance with national requirements, whichever is longer.

Since off-site storage is used, a study-specific binder will remain at the site after the other study-specific documents have been shipped for off-site storage. This binder is considered part of the investigator TMF and must be kept in a secure place by the site for the required period of time. The binder must contain, at a minimum, the following documents: a copy of the *Investigator TMF Index*, a certified copy of the *Patient Identification Code List*, and a *Retrieval Form*.

Lundbeck will notify the investigator in writing when the required storage period has expired and when the documents may be destroyed according to regulations.

## **12 Monitoring Procedures**

Prior to including patients in the study, the investigator must sign a source data agreement that identifies the source documents (original documents, data, and records) at the site. The document will also list which data may be recorded directly on the eCRFs or any electronic clinical outcome assessment electronic clinical outcome assessment (eCOA).

If the investigator does not have a patient's medical records, the investigator must attempt to obtain copies or a written summary of relevant medical records from the doctor who had treated the patient earlier and include the pertinent documentation in the patient's medical records at the site. The investigator must obtain medical records documenting the patient's lifetime (schizophrenia) episodes and general medical history for the 3 months prior to the study.

During the study, the CRA will visit the site to ensure that the protocol is being adhered to and that all issues are being recorded, to perform source data verification, and to monitor IMP accountability. The visit intervals will depend on the outcome of the remote monitoring of the eCRFs, the site's recruitment rate, and the compliance of the site to the protocol and *Good Clinical Practice*. In addition, the CRA will be available for discussions by telephone.

Source data verification requires that the CRA be given direct access to all the source documents. Direct access includes permission to examine, analyse, and verify any records and reports that are important for the evaluation of the study.

## 13 Audits and Inspections

Authorised personnel from Global Clinical Quality Assurance at Lundbeck and quality assurance personnel from business partners may audit the study at any time to assess compliance with the protocol and the principles of *Good Clinical Practice* and all other relevant regulations.

The patients must be informed that authorised personnel from Lundbeck may wish to review their medical records. The investigator must be aware and the patients must be informed that representatives from regulatory authorities may also wish to inspect source data, such as medical records.

The investigator must notify Lundbeck, without delay, of an announced inspection by a regulatory authority.

During audits and inspections, the investigator must permit direct access to all the source documents, including medical records and other documents pertinent to the study.

During audits and inspections, the auditors and inspectors may copy relevant parts of medical records. No personal identification apart from the screening number will appear on these copies.

Patient data will not be disclosed to unauthorised third parties, and patient confidentiality will be maintained at all times.

## 14 Protocol Compliance

Lundbeck has a “no-waiver” policy, which means that permission will not be given to deviate from the protocol.

If deviations occur, the investigator must inform the CRA and they must review, discuss, and document the implications of the deviation.

## 15 Study Termination

Lundbeck or a pertinent regulatory authority may terminate the study or part of the study at any time. The reasons for such action may include, but are not limited to:

- safety concerns
- proven lack of efficacy of the IMP in other studies

If the study is terminated or suspended, the investigator must promptly inform the patients and ensure appropriate therapy and follow-up. Furthermore, the investigator and/or sponsor must promptly inform the IEC or IRB and provide a detailed written explanation. The pertinent regulatory authorities must be informed in accordance with national regulations.

If the risk/benefit analysis changes after the termination of the study, the new evaluation must be provided to the IEC or IRB if it will have an impact on the planned follow-up of the patients who participated in the study. If so, the actions needed to protect the patients must be described.

## 16 Endpoints

### 16.1 Primary Endpoint(s)

- Primary safety and tolerability endpoints:
  - Adverse events
  - Absolute values, changes values from baseline and potentially clinically significant values in:
    - Clinical safety laboratory tests
    - Body weight, BMI, and waist circumference
    - Vital signs (systolic blood pressure, diastolic blood pressure, and pulse)
    - ECG parameters (ventricular rate, RR, PR, QRS, QT, and QTcF)

### 16.2 Exploratory Endpoint(s)

- Exploratory safety and tolerability endpoints:
  - Mean change from baseline in AIMS, BARS and mSAS total scores
  - C-SSRS categorisation
- Exploratory effectiveness endpoints:
  - Psychotic symptoms
    - Mean change from baseline in PANSS total score
    - Mean change from baseline in PANSS subscale scores (PANSS Negative Symptoms subscale, PANSS Positive Symptoms subscale, PANSS General Psychopathology subscale)
  - Negative symptoms
    - Mean change from baseline in NSA-4 total score
  - Global clinical impression
    - Mean change from baseline in CGI-S score
  - Andreason symptoms remission rate
    - Binary variable (Y/N) of remission rate (simultaneous ratings of mild or less on PANSS specific items: P1, G9, P3, P2, G5, N1, N4, and N6) at Week 52 Visit
  - Quality of life and functioning
    - Mean change from baseline in QLS score
    - Mean change from baseline in Tool score
    - Mean change from baseline in WorQ score
    - Mean change from baseline in PSP total score

- Treatment satisfaction
  - Mean change from baseline in MSQ score
- Health care resource used during the 52-week study period

## 17 Statistical Methodology

### 17.1 Responsibilities

The Department of Biostatistics, H. Lundbeck A/S will perform the statistical analyses described below.

### 17.2 Analysis Sets

The following analysis sets are defined.

- all-patients-treated set (APTS) – all patients who took at least one dose of Lu AF35700 in study 16159B.
- full analysis set (FAS) – all patients in the APTS who had at least one valid post baseline effectiveness assessment in study 16159B.

The APTS will mainly be used for presentations of safety data whereas the FAS will be used for effectiveness data.

### 17.3 Descriptive Statistics

In general, summary statistics (n, arithmetic mean, standard deviation, median, minimum and maximum values) will be presented for continuous variables and counts and, if relevant, percentages will be presented for categorical variables.

For patients coming from 16159A, summaries will be prepared with respect to two baselines:

- Baseline I: Baseline just prior to randomisation in study 16159A (Baseline 2 in 16159A)
- Baseline II: Baseline in study 16159B.

Unless otherwise specified, baseline will be Baseline II.

Summaries will be prepared overall and by the previous treatment (treatment group in the studies feeding into this extension study or previous treatment for patients not included in any Lu AF35700 study before). In order not to have too many “previous treatments”, these will be grouped into the following categories:

- Lu AF35700
- Risperidone/Olanzapine (16159A patients)
- Quetiapine
- Previous treatment for patients not included in any Lu AF35700 study before

To explore the safety and effectiveness of daily dosing with Lu AF35700, separate displays will be prepared for patients only receiving daily dosing in this study.

#### **17.4 Patient Disposition**

Patient disposition will be summarised by reason for withdrawal and other relevant parameters and include the number of patients who completed and the number of patients who withdrew from the study.

#### **17.5 Demographics and Other Baseline Characteristics**

Demographics (sex, age, race), and other baseline characteristics will be summarised.

#### **17.6 Recent and Concomitant Medication**

Recent and concomitant medication will be summarised by anatomical therapeutic chemical (ATC) code and generic drug name.

#### **17.7 Exposure and Compliance**

Exposure and compliance will be calculated per patient and summarised.

In particular, the amount of weekly dosing, frequency, duration, and reasons for initiation and termination, will be summarised.

#### **17.8 Effectiveness Analyses**

Effectiveness assessment will be summarised descriptively using Observed Cases (OC). Summaries will be performed with respect to both Baseline I and Baseline II. On an exploratory basis, the maintenance of effectiveness will be analysed using Mixed Models for Repeated Measurements (MMRM).

Quality of life, treatment satisfaction and health care resource utilization will be summarised.

Based on the FAS and observed cases (OC), the effectiveness endpoints will be analysed using a mixed model for repeated measurements (MMRM) with an unstructured covariance structure. The model will include terms for country, baseline 1/2 score visit, and previous treatment.

## 17.9 Safety Analyses

### 17.9.1 Analysis of Adverse Events

Adverse events will be classified according to the time of onset of the adverse event:

- *pre-study adverse event* – an adverse event that starts before the date of first dose of IMP in study 16159B.
- *Treatment-emergent adverse event (TEAE)* – an adverse event that starts or increases in intensity on or after the date of first dose of Lu AF35700 in study 16159B.

Adverse events, sorted by system organ class (SOC) and preferred term, will be summarised.

Specific tables of adverse events after weekly dosing will be prepared. Displays of all events while on weekly dosing, as well as events seen shortly after initiation of weekly dosing will be prepared.

#### Allocation of TEAEs to Treatment Periods

TEAEs may be allocated into study periods (these will be defined in the *Statistical Analysis Plan*).

Where relevant, Kaplan-Meier plots of time to TEAEs, will be prepared.

### 17.9.2 Analysis of Other Safety Endpoints

The clinical safety laboratory test values, body weight, BMI and waist circumference, vital signs, and ECG parameters will be summarized. Potentially clinically significant (PCS) values will be flagged and summarized.

Mean change from baseline in AIMS, BARS and mSAS total scores will be summarized.

The C-SSRS will be summarized descriptively.

## 17.10 Interim Analyses

No interim analyses are planned.

## 17.11 Sample Size and Power

No formal sample size calculation has been performed for the present study.

Approximately 400 patients with schizophrenia are planned to be enrolled in total in order to provide relevant long-term safety data. It is assumed that about 270 patients will come from study 16159A, 30 patients from study 16323A, and an additional 100 patients who need to change their antipsychotic treatment will be included. The distribution of the number of patients may be adjusted based upon the recruitment rate in each group. With approximately

400 patients included, it will be possible to obtain solid information on long-term safety of treatment with Lu AF35700.

To ensure sufficient exposure to the daily dosing regimen, the number of patients who completed study 16159A and who can be treated with the weekly dosing regimen will be limited to 50 patients.

### **17.12 Statistical Analysis Plan**

A *Statistical Analysis Plan* describing the handling of data issues and the planned statistical analyses in more detail will be prepared by the Department of Biostatistics, H. Lundbeck A/S.

## **18 Clinical Study Report and Publications**

### **18.1 Clinical Study Report**

Upon completion of the study, a *Clinical Study Report* will be prepared by the Department of Medical Writing, H. Lundbeck A/S.

### **18.2 Data Ownership**

The data collected in this study are the property of Lundbeck.

### **18.3 Publications**

The results of this study will be submitted for publication.

The primary publication based on this study must be published before any secondary publications are submitted for publication.

Authors of the primary publication must fulfil the criteria defined by the International Committee of Medical Journal Editors (ICMJE).

## **19 Indemnity and Insurance**

In the event of study-related injuries or deaths, insurance for the patients and indemnity of the investigators and those of their employees, servants, or agents whose participation in this study has been documented are provided. Insurance and liability will be in accordance with applicable laws and *Good Clinical Practice*.

## **20 Finance**

### **20.1 Site Agreement**

The financial agreements for the site are addressed in one or more documents. Both parties must sign the agreements before the site is initiated.

### **20.2 Financial Disclosure**

All the investigators, including sub-investigators, and raters participating in the study must complete a *Financial Disclosure Form* in order to comply with the United States Food and Drug Administration (FDA) *Financial Disclosure* requirements.

### **20.3 Equipment**

Equipment owned or rented by Lundbeck that has been provided to the site for use during the study must be returned at the end of the study.

**Appendix II**  
**Recent and Concomitant Medication:**  
**Disallowed or Allowed with Restrictions**

## Recent and Concomitant Medication: Disallowed or Allowed with Restrictions

In the table below disallowed recent and concomitant medications are listed, including any restrictions with respect to their use prior to and during the study.

### Disallowed and restricted medications during the study

Drug Class	Details
Analgesics	
 
– Opioid analgesics are not allowed, except for brief episodic use during emergency procedures or appropriate indication (e.g. tooth extraction) and not within 24 hour before a study visit.
 
– NSAIDs are prohibited as chronic use; NSAIDs may be used episodically.
 

Anticholinergics	
 
– The use of anticholinergic medication as prophylaxis of extrapyramidal symptoms should be avoided.
 
– In case of need of rescue medication, the use of multiple anticholinergic medications concurrently is prohibited.
 
– The allowed rescue medications are the following: benzotropine (up to 4 mg/day p.o. or i.m.), biperiden (up to 8 mg/day p.o. or i.m.) and thihexyphenidyl (up to 10 mg/day p.o. or i.m.).
 
– Administration of anticholinergics less than 8 hours prior a scheduled visit is not allowed.
 

Anticonvulsants	
 
– Prohibited during the study
 

Antidepressants	
 
– Prohibited during the study
 

Antihistamines	
 
– Antihistamines except loratadine, desloratidine, cetirizine, levocetirizine, mizolastine and fexofenadine are prohibited.
 

Antipsychotics	
 
– Depot or long-acting injectable antipsychotics are not allowed as current treatment.
 
– Current oral antipsychotics to be down tapered and discontinued as indicated in Panel 3.
 
– Oral antipsychotics other than LuAF35700 is disallowed during the study.
 

Anxiolytics and hypnotics	
 
– If the patient receives anxiolytic or hypnotic therapy during study 16159A, this medication may continue. A careful down tapering of anxiolytic or hypnotic treatment should be performed if a discontinuation has been decided.
 
– In case of need of rescue medication for anxiety, dose adjustment of currently prescribed anxiolytic medication is recommended if applicable. If new medication is initiated, short-acting benzodiazepines such as lorazepam (up to 3 mg/day, orally or intramuscularly), oxazepam (up to 45 mg/day, orally), and alprazolam (up to 1.5 mg/day) are recommended.
 
– In case of need of rescue medication for sleep disorders, short acting hypnotics such as zolpidem (up to 5 mg/day for immediate release formulations and 6.25 mg/day for extended release formulations, orally) and zopiclone (up to 7.5 mg/day) are recommended.
 
– Administration of anxiolytics or hypnotics less than 8 hours prior a scheduled visit is not allowed.
 

Barbiturates	
 
– Prohibited during the study
 

Drug Class	Details
Dopamine depleting agents	– Prohibited during the study
Hormones	– Prohibited except for thyroid hormone replacement, contraceptives (oral, patch), estrogen and progesterone replacement therapy as well as benign prostatic hyperplasia treatment.
Hydroxyzine and diphenhydramine (not allowed for the treatment of agitation, anxiety, insomnia or EPS)	– Except for short term treatment (<14 days) of allergy.
Mood stabilizers	– Prohibited during the study
Non-benzodiazepine sleep aids	– Prohibited during the study
Propranolol (for akathisia or tremor)	
 
– Prophylaxis treatment should be avoided.
 
– In case of need of rescue medication a maximum dose of 60 mg/day is allowed.
 
– If propranolol is prescribed for cardiovascular reasons at doses greater than 60 mg/day, the eligibility of the patients should be discussed with the Medical Monitor.
 
– Administration of propranolol less than 8 hours of a scheduled visit is not allowed.
 

Psychotropic agents not otherwise specified	
 
– Prohibited during the study
 
– Cough preparations containing ephedrine, pseudoephedrine and codeine are allowed for treatment duration for a maximum of 1 week.
 

Steroids	– Systemic use is prohibited, inhaled and topical use is allowed.
Varenicline	– Prohibited during the study
Vitamins, nutritional supplements, and non-prescription herbal preparations	– Prohibited during the study, unless approved in advance by the Medical Monitor.

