#### Inclusion Criteria

##### For patients who completed study 16159A

Patients who meet each of the inclusion criteria and none of the exclusion criteria at the Baseline Visit (unless otherwise specified; some criteria assessed as part of the Primary Outcome Visit in study 16159A) are eligible to participate in this study.

1. The patient has completed study 16159A.
2. The patient is still capable of communicating with the site personnel.
3. The patient and if applicable his or her legal representative is/are able to read and understand the *Informed Consent Form*.
4. The patient and if applicable his or her legal representative has/have signed the *Informed Consent Form* for study 16159B.
5. The patient is willing and able to attend study appointments within the specified time windows.
6. The patient can potentially benefit from 52-week treatment with Lu AF35700 according to the investigator's clinical judgment.
7. The patient has a caregiver or an identified responsible person considered reliable by the investigator (for example, family member, social worker, case worker, or nurse) considered reliable by the investigator in providing support to the patient to ensure compliance with study treatment, outpatient visits, and protocol procedures.
8. The patient has a stable living environment, as demonstrated by the ability to provide contact information for themselves and/or family/friend(s)/caregiver(s).
9. The patient, if a woman, must:
  - agree not to try to become pregnant during the study, AND
  - use adequate, highly effective contraception (defined as those that result in a low failure rate [that is, <1% per year] when used consistently and correctly, for example, implants, injectables, combined oral contraceptives in combination with a double barrier method, some intrauterine devices, sexual abstinence, vasectomised partner), OR
  - have had her last natural menstruation  $\geq 28$  months prior to the Primary Outcome Visit in study 16159A, OR
  - have been surgically sterilised prior to the Primary Outcome Visit in study 16159A, OR
  - have had a hysterectomy prior to the Primary Outcome Visit in study 16159A.
10. The patient, if a man, must:
  - use two methods of contraception in combination if his female partner is of childbearing potential; this combination of contraceptive methods must be used from the Baseline Visit to  $\geq 3$  months after the last dose of IMP, OR

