  - use adequate, highly effective contraception (defined as those that result in a low failure rate [that is, <1% per year] when used consistently and correctly, for example, implants, injectables, combined oral contraceptives in combination with a double barrier method, some intrauterine devices, sexual abstinence, vasectomised partner), OR
  - have had her last natural menstruation  $\geq 28$  months prior to the Primary Outcome Visit in study 16323A, OR
  - have been surgically sterilised prior to the last visit of the dosing period in study 16323A, OR
  - have had a hysterectomy prior to the last visit of the dosing period in study 16323A.

10. The patient, if a man, must:
  - use two methods of contraception in combination if his female partner is of childbearing potential; this combination of contraceptive methods must be used from the Baseline Visit to  $\geq 3$  months after the last dose of IMP, OR
  - have been surgically sterilised prior to the last visit of the dosing period in study 16323A.
11. The patient has a confirmed diagnosis of schizophrenia according to DSM-5TM.
12. The patient is willing to discontinue all prohibited psychotropic medications to meet protocol-required washout prior and during the study.

*For patients who can potentially benefit from treatment with Lu AF35700*

Patients who meet each of the inclusion criteria at the Screening and Baseline Visits (unless otherwise specified) and none of the exclusion criteria at the Screening and Baseline Visits (unless otherwise specified) are eligible to participate in this study.

1. The patient is capable of communicating with the site personnel.
2. The patient and if applicable his or her legal representative is/are able to read and understand the *Informed Consent Form*.
3. The patient and if applicable his or her legal representative has/have signed the *Informed Consent Form* for study 16159B.
4. The patient is willing and able to attend study appointments within the specified time windows.
5. The patient is either an inpatient at a psychiatric setting or outpatient consulting a psychiatrist.
6. The patient has schizophrenia, diagnosed according to DSM-5TM.
7. The patient is a man or woman, aged  $\geq 18$  years.
8. The patient has been prescribed an oral antipsychotic treatment at recommended dose range as stated in the SmPC or equivalent document/label for 6 weeks prior the Screening Visit.

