#### Medical

12. The patient has any other medical disease for which the treatment takes priority over treatment of schizophrenia or is likely to interfere with study treatment or impair treatment compliance.
13. The patient has a moderate or severe ongoing adverse event related to IMP from study 16159A considered of potential safety risk by the investigator.
14. The patient takes or has taken disallowed recent or concomitant medication (specified in [Appendix II](#)) in study 16159A.
15. The patient has a disease or takes medication that could, in the investigator’s opinion, interfere with the assessments of safety, tolerability or efficacy, or interfere with the conduct or interpretation of the study.
16. The patient has clinically significant abnormal vital signs considered of potential safety risk by the investigator.
17. The patient has one or more laboratory values outside the reference range, based on the last available blood or urine samples taken during study 16159A that are, in the investigator’s opinion, of potential risk to the patient’s safety, or the patient has any of the following values at study 16159A (the medical monitor should be contacted in case of uncertainty):
  - a serum creatinine value >1.5 times the upper limit of the reference range
  - a serum total bilirubin value >1.5 times the upper limit of the reference range
  - a serum alanine aminotransferase (ALT) or aspartate aminotransferase (AST) value >2 times the upper limit of the reference range
18. The patient has not previously been diagnosed with diabetes, but meets ANY of the following criteria (newly diagnosed diabetes) based on the last available blood samples taken during study 16159A:
  - HbA1C >6.5%, OR
  - fasting plasma glucose >126 mg/dL (7.0 mmol/L), OR
  - non-fasting plasma glucose >200 mg/dL (11.1. mmol).
19. The patient has previously been diagnosed with diabetes, but the condition is unstable as determined by ANY of the following criteria based on the last available blood samples taken during study 16159A:
  - HbA1c ≥7.0%, OR
  - glucose >6.94 mmol/L (fasting, >125 mg/dL) or 11.1 mmol/L (nonfasting, 200 mg/dL)

- any other abnormal laboratory tests that in the investigator’s clinical judgement are medically significant and would impact on the safety of the patient or the interpretation of the study results.

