**For patients who can potentially benefit from treatment with Lu AF35700**

General

1. The patient has previously been enrolled in this study.
2. The patient has participated in a clinical study <30 days prior to the Screening Visit.
3. The patient is a member of the study personnel or of their immediate families, or is a subordinate (or immediate family member of a subordinate) to any of the study personnel.
4. The patient is under forced treatment.
5. The patient is pregnant or breast-feeding.
6. The patient has a history of severe drug allergy or hypersensitivity, or known hypersensitivity to any of the IMP(s) or its/their excipients.
7. The patient has a disease or takes medication that could, in the investigator's opinion, interfere with the assessments of safety, tolerability, or efficacy, or interfere with the conduct or interpretation of the study.
8. The patient takes or has taken disallowed recent or concomitant medication (specified in [Appendix II](#)) or it is anticipated that the patient will require treatment with at least one of the disallowed concomitant medications during the study.
9. The patient is, in the investigator's opinion, unlikely to comply with the protocol or is unsuitable for any reason.

Psychiatric

10. The patient has any current psychiatric disorder (DSM-5™ criteria) other than schizophrenia established as the primary diagnosis.
11. The patient suffers from intellectual disability, organic mental disorders, or mental disorders due to a general medical condition (DSM-5™ criteria).
12. The patient is experiencing acute exacerbation of his/her psychotic symptoms at the Screening Visit, between the Screening and Baseline Visits or at the Baseline Visit according to the investigator's judgment.
13. The patient is treated with clozapine at the time of the Screening Visit.
14. The patient has a current diagnosis or a history of substance use disorder according to DSM-5™ criteria within 6 months prior to the Screening Visit with the exception of tobacco, or mild cannabis or mild alcohol use disorder. Patients with a positive drug screen test with the exception of cannabis and verified by repeated testing are excluded from the study.

15. The patient is at significant risk of harming himself/herself or others according to the investigator's clinical judgement, or who on the C-SSRS:
  - Answers "Yes" to questions 4 or 5 on the Suicidal Ideation section within the last 3 months at Screening, OR

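### Appendix II, on its natural reading, prohibits hormonal implants, hormonal injectables and hormone-releasing intrauterine devices, although the inclusion criteria accept these types of contraception (low severity)

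*Protocol*

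**What the plan says.** **Contraception accepted.** Protocol section 5.3 requires a woman to use highly effective contraception unless she is postmenopausal, surgically sterilised or has had a hysterectomy. All three patient groups have the same examples: "for example, implants, injectables, combined oral contraceptives in combination with a double barrier method, some intrauterine devices, sexual abstinence, vasectomised partner". This is criterion 9 for 16159A-patients and for 16323A-patients, and criterion 16 for Other Patients.

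**Hormones disallowed.** The Hormones row of the Appendix II table says "Prohibited except for thyroid hormone replacement, contraceptives (oral, patch), estrogen and progesterone replacement therapy as well as benign prostatic hyperplasia treatment". The table is headed "Disallowed and restricted medications during the study".

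**Link to eligibility.** Exclusion criterion 14 for each lead-in group, and exclusion criterion 8 for Other Patients, begin "The patient takes or has taken disallowed recent or concomitant medication" and point to Appendix II. Criterion 8 adds the case where "it is anticipated that the patient will require treatment with at least one of the disallowed concomitant medications during the study".

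**How the lists combine.** For both lead-in groups, those eligible are "Patients who meet each of the inclusion criteria and none of the exclusion criteria at the Baseline Visit". The rule for Other Patients is the same in substance: "Patients who meet each of the inclusion criteria at the Screening and Baseline Visits (unless otherwise specified) and none of the exclusion criteria".

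**The concern.** Two operative eligibility rules treat the same contraceptive differently. One names it as adequate protection. The other, followed to the letter, makes it a disallowed hormone and so a ground for exclusion.

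A woman could be refused the extension, or be in breach during it, for using a method that the protocol itself puts forward for preventing pregnancy. Pregnancy is a reason for withdrawal from treatment (section 5.4), so the protocol has no evident interest in discouraging effective methods. Section 14 rules out waivers, so an investigator who notices the mismatch cannot be given permission to set it aside.

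**Working it through.** No figure in the plan bears on this point, so the check is a comparison of the texts.

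**Step 1. Is the contraceptive exemption a closed list?** The Hormones row gives two routes in brackets with no word marking them as examples. Elsewhere the appendix does mark examples: the Analgesics row uses *e.g.*, and the Anxiolytics and hypnotics row uses *such as*. The Antihistamines row has the same prohibited-except structure, with six named drugs, and is plainly exhaustive. The closed reading is therefore the natural one, though not certain.

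**Step 2. Does another exemption cover these methods?** The row also allows oestrogen and progesterone replacement therapy. That names replacement, not contraception. No other text in the protocol or SAP extends the contraceptive exemption.

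**Step 3. Compare the six inclusion examples with the row.**

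| Example in criterion 9 / 16 | Status under the Hormones row, closed reading |
|---|---|
| Implants | Prohibited if hormonal |
| Injectables | Prohibited if hormonal |
| Some intrauterine devices | Prohibited only if hormone-releasing |
| Combined oral with double barrier | Allowed (oral) |
| Sexual abstinence | Not a hormone |
| Vasectomised partner | Not a hormone |

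Count: 2 in conflict if hormonal + 1 in conflict only if hormone-releasing + 3 not in conflict = 6. The lists also differ in the other direction: the patch is exempt in Appendix II but is not among the inclusion examples.

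**Step 4. Apply the eligibility rule.** A current user of a hormonal implant meets the contraception criterion. She also takes a hormone outside the exemptions, so exclusion 14 (or 8) applies. Since no exclusion criterion may be met, the exclusion prevails. If she is already in the study, she is on a prohibited medication.

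**Step 5. Who is reached?** All three inclusion lists and all three exclusion lists carry the conflict. SAP section 2 says that patients without earlier participation were never enrolled, so criteria 16 and 8 had no effect on the enrolled population. Both lead-in groups remain. Most patients came from 16159A, and four from 16323A (SAP section 5). Those four appear only in listings, but the same inclusion 9 and exclusion 14 governed their entry.

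**Step 6. What follows downstream?** Section 5.4 has no withdrawal criterion specific to disallowed medication; only the general one on failing to comply with study procedures could apply. SAP section 5 defines no analysis set by protocol deviations, so no planned analysis changes.

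**The case against.** **The bracket may be illustrative.** The same row allows hormone replacement with no limit on route, so it shows no evident wish to keep such hormones out of a contraceptive implant. This stands as evidence that the bar was not intended. It does not supply an exemption, and a site checking the row as written would still find only oral and patch.

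**This is not a logical contradiction.** The inclusion methods are only examples, and a patient may ordinarily meet an inclusion criterion and fail an exclusion criterion. That is correct: the literal outcome is determinate, and two sites would decide differently only if one of them overlooked the appendix. The defect is that the determinate outcome rejects a method the protocol has just put forward as adequate.

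**The conflict is conditional.** A reader might infer that every implant, injectable or intrauterine device is barred. The documents do not support that: the row concerns hormones, and they do not say which of these products are hormonal.

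**Past use.** A reader might also infer that changing method at roll-over would not help, because exclusion 14 reaches medication taken during the lead-in study. The introduction to Appendix II does mention restrictions before as well as during the study. But the Hormones row states no washout or prior-use limit, and the table heading speaks of the study itself. The point is therefore confined to current use.

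**Little is at stake.** Compliant methods remain, and SAP section 2 already describes enrolment in the past tense, so an amendment cannot undo a refusal. This stands, and it is why the point is rated low.

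**Conclusion.** The text is wrong as written, at low severity. A woman currently using a hormonal implant, a hormonal injectable or a hormone-releasing intrauterine device is barred, or is on a prohibited medication, by a row that conflicts with the contraception criterion she meets.

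This rests on two assumptions: that the bracket in the Hormones row is a closed list, and that the product is hormonal. The first is the natural reading. The second is the ordinary meaning for implants and injectables, and holds for only some intrauterine devices.

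The number of women affected is unknown and may be near zero. The documents give no sex split, no contraceptive use and no hormone rule for either lead-in study. A reader might take the enrolled total as the scale of the problem: SAP section 16 gives more than 500 patients. That figure does not measure it, because it counts both sexes and leaves out any woman who was refused. The concomitant medication tables in SAP section 9 would help only in part. They are based on treated 16159A patients, so they cannot show refusals, and they are organised by ATC code and generic name rather than by route.

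**What to change.** In the Appendix II Hormones row, replace the contraceptive item with: *hormonal contraceptives (oral, patch, implant, injectable, hormone-releasing intrauterine device)*. Do not tie the exemption to criterion 9 or 16. The patch is not among their examples, and their oral example requires a double barrier, so a cross-reference could narrow what the row now allows.

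If the sponsor did mean to prohibit these methods, the examples in criteria 9, 9 and 16 should be cut back to permitted ones instead.

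The cost is a minor protocol amendment, with notification of the ethics committee or review board where required (section 4.4). It needs no new procedure and no change to any analysis. Made late, it would help only women still on treatment.
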